## 5.6 Follow-Up for Subject Withdrawal from Study

To minimize missing data for efficacy and safety assessments, subjects who prematurely discontinue study drug treatment should continue to be followed for all regularly scheduled visits, unless subjects have decided to discontinue the study participation entirely (withdrawal of informed consent). Subjects should be advised on the continued scientific importance of their data even if they discontinue treatment with study drug early.

If a subject prematurely discontinues study participation (withdrawal of informed consent), the procedures outlined for the Premature Discontinuation visit (PD visit) should be completed as soon as possible, preferably within 2 weeks. In addition, if subject is willing, a 30-day follow-up phone call after the last dose of study drug may be completed to ensure all treatment-emergent AEs/serious adverse events (SAEs) have been resolved.

All attempts must be made to determine the date of the last study drug dose and the reason for discontinuation of study drug or study participation. The information will be recorded on the appropriate eCRF page. However, these procedures should not interfere with the initiation of any new treatments or therapeutic modalities that the investigator considers necessary to treat the subject's condition. Following discontinuation of study drug, the subject will be treated in accordance with the investigator's best clinical judgment, irrespective of whether or not the subject decides to continue participation in the study.

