# **WEEK 24/**

### **PREMATURE**

DISCONTINUATION:

□ INTERVIEW	

AE assessment

Concomitant therapy

Birth control attestation

	
 
Contraceptive counseling/dispense nonhormonal contraceptives as necessary
 
Review e-Diary entries
 

PRO EXAM	
 
C-SSRS Since Last Visit
 
MBQ
 
Physical exam
 
Weight and waist circumference
 
Vital signs
 
Gynecological (pelvic and breast) exam
 
Acne lesion assessment and IGA
 
	
 
PCOSQ
 
PGIA and PGIH
 
MRI if required
 
Pelvic ultrasound (TVU and TAU)
 
Urine pregnancy test
 
DXA scan
 
FG Score
 

A CENTRAL LAB	
 
Endocrine hormones/test:
 
Fasting insulin
 
HbA1c
 
Androstenedione
 
AMH
 
Testosterone/SHBG
 
E2
 
Progesterone
 
	
 
Clinical laboratory test (chemistry, hematology, lipid panel, urinalysis)
 
Liver transaminases (ALT, AST) and fractionated bilirubin
 
Elagolix single PK sample
 
LH/FSH single PD sample
 
Serum pregnancy test
 
Optional biomarker sample: whole blood (DNA and RNA), serum, plasma
 

R TREATMENT	
 
Review subject dosing and perform drug reconciliation
 
	7.0

NOTE: If the Premature Discontinuation visit takes place at or before Week 12, a DXA scan would not be required.

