#### Dual Energy X-ray Absorptiometry (DXA)

DXA scans of the lumber spine, femoral neck, and total hip will be performed at the time points specified in Section 2. Site training and qualifications, which include assessment of instruments, will be evaluated/approved by the central reader prior to screening of the first subject. Instructions on calibration and standardization of instruments and any additional required information will be specified in a manual from the central reader that will be provided to all study sites. Sites will need to obtain approval from the central reader prior to initiating study scans.

The screening DXA scan will be sent to the central reader to determine eligibility and serve as the baseline scan for subject management.

During the Treatment Periods, DXA scans will be performed for all subjects at Week 24 and will be submitted to the central reader for review and analysis. DXA scans will only be performed at the PD Visit if the subject has received study drug for at least 12 weeks.

DXA scans will be performed by qualified technologist/radiologists at the site or affiliated imaging facility using GE Lunar or Hologic equipment and per the acquisition guidelines provided by the Central Imaging Core Lab (central reader). The DXA technologist/radiologist or designee for each investigative site

should electronically submit the subject's DXA images to the central reader for review and analysis following acquisition. The central reader will be blinded to the subject's treatment assignment, but not to the corresponding time point.

Subject eligibility will be made based on the central reader review. Sites will receive reports from the central reader that detail the results (including Z-scores and bone mineral density (BMD) % change from Baseline, as applicable) of the DXA scans performed.

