8.2 Handling of Missing Data

Missing data will be imputed using the following methods for the efficacy analyses:

Mixed-Effect Model Repeat Measurement (MMRM): The repeated measures analyses will be conducted using mixed models including observed measurements at all visits. The mixed model includes the categorical fixed effects of treatment, visit and treatment-by-visit interaction, subject as a random effect, and the continuous fixed covariates of baseline measurement. An unstructured variance covariance matrix will be used. Parameter estimation is based on the assumption of data being missing at random and using the method of restrictive maximum likelihood (REML). Missing data will not be imputed for MMRM analysis.

Observed Cases (OC): The OC analysis will not impute values for missing evaluations, and thus a subject who does not have an evaluation on a scheduled visit will be excluded from the OC analysis for that visit. OC will exclude values after a subject prematurely discontinues from study drug.

Multiple Imputation (MI): The MI approach will be used as a sensitivity analysis for the primary endpoint. For the primary endpoint, 20 'complete' datasets will be generated using SAS PROC MI. The seed will be 123. Using the Cochran-Mantel-Haenszel (CMH) model adjusted for FG score ($< 8, \geq 8$) and normal/obese status ($BMI < 30, \geq 30$) at Baseline, the imputed endpoints will be analyzed using each of the 20 datasets. SAS PROC MIANALYZE will be used to generate the final inferences of difference of proportion of menstrual cycle responders between each elagolix group and placebo.

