9.0 Safety Analyses

9.1 General Considerations

Safety analyses will be carried out using Safety Analysis Set. All safety analyses will be based on observed data. Unless otherwise specified, missing data will not be imputed.

For continuous variables, when the analyses of change and/or percent change from Baseline to post-baseline visit(s) are performed, the within-group change from Baseline to each relevant visit will be summarized by treatment group with the mean, SE, and 95% CIs. The between-group differences will be summarized with the mean, SE, 95% CIs, and P value when applicable. P value will be compared to an alpha level of 0.05. At each post-baseline visit, the Baseline mean and post-baseline visit mean will be calculated for all subjects with baseline and post-baseline value at that visit by treatment group.

Categorical data will be summarized by number and percentage of subjects by treatment group.

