9.5.2 Bone Mineral Density

All analyses and summaries of bone mineral density (BMD) will be performed for each segment, i.e., femoral neck, lumbar spine, and total hip. For subjects who had a right-side scan performed (rare instances), their data for right femoral neck and right femoral total hip will be included in the analysis with the data for the left femoral neck and left total hip, respectively (available for the majority of subjects). If more than one scan is reported for an anatomical segment within an analysis window, the worse (the lower value) of the multiple measurements will be used for analysis for each anatomical segment. The analyses below will exclude subjects who switch machine manufacturer types between baseline and post-baseline.

A continuous summary of BMD at Baseline and Month 6 will be provided by treatment group. This summary will include the mean, SD, median, minimum, and maximum.

The analysis of percent change from baseline in BMD during the Treatment Period will be based on an ANCOVA model with treatment as the main effect and baseline value of

corresponding parameter as a covariate. Each elagolix group will be compared to placebo.

The number and percentage of subjects with percent change from Baseline to Month 6 during the Treatment Period in mutually exclusive categories of BMD decrease: $\leq 0\%$, $> 0\% - \leq 1.5\%$, $> 1.5\% - \leq 3\%$, $> 3\% - \leq 5\%$, $> 5\% - < 8\%$, and $\geq 8\%$ will be summarized by treatment group. The comparison between each elagolix group and placebo will be made using Fisher's exact test.

A listing of subjects with BMD decrease from baseline $\geq 8\%$ will be provided.

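### SAP 9.5.2 sets no limit on time since last dose for BMD scans, so Week 24 scans taken off drug enter the Month 6 analyses, and no on-treatment BMD result is planned

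*SAP*

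**What the plan says.** **Who is scanned.** Protocol 5.6 says that "subjects who prematurely discontinue study drug treatment should continue to be followed for all regularly scheduled visits", unless consent is withdrawn. It ties the Premature Discontinuation (PD) visit to ending study participation. Operations Manual 3.17 adds: "During the Treatment Periods, DXA scans will be performed for all subjects at Week 24". That sentence carries no exposure condition. The PD visit scan does carry one: "DXA scans will only be performed at the PD Visit if the subject has received study drug for at least 12 weeks". The visit note in Operations Manual 2.2 words it differently: "If the Premature Discontinuation visit takes place at or before Week 12, a DXA scan would not be required".

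**What is analysed.** SAP 9.1 says: "All safety analyses will be based on observed data". SAP 4.0 groups safety data by treatment received. SAP 9.5.2 plans the Month 6 summary ("A continuous summary of BMD at Baseline and Month 6 will be provided by treatment group"), an ANCOVA of percent change from baseline during the Treatment Period, and categories of percent decrease to Month 6. Its only stated exclusion of subjects is: "The analyses below will exclude subjects who switch machine manufacturer types between baseline and post-baseline". It refers to an analysis window for BMD but gives no days and no link to the last dose.

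**Rules elsewhere.** In SAP 8.2, "OC will exclude values after a subject prematurely discontinues from study drug". That rule belongs to the Observed Cases method for efficacy and is not repeated in SAP 9. The hepatotoxicity summary in SAP 9.3 uses maximum on-treatment values.

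**The concern.** Protocol 4.2 gives the purpose of DXA as assessing the effect of elagolix therapy on BMD. BMD is a safety endpoint (Protocol 3.5), and BMD decrease is an adverse event of special interest (Protocol 6.1). A woman who took drug for a few weeks and was scanned months later says little about bone loss on 24 weeks of treatment. As written, however, she counts the same as a woman who took drug throughout.

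If loss builds with time on drug, such scans bias the elagolix mean toward placebo, which is the unfavourable direction for a safety comparison. Each elagolix arm has 20 women, so 4 of them are 20% of an arm. In a trial of five active regimens, unequal early stopping could also blur the dose ordering of bone loss. No planned BMD output shows how long each woman had been off drug at her scan, so a reader of the report could not judge the effect.

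**Working it through.** **Step 1. Is there a plan figure to reproduce?** Not for BMD. The only power figure is for the primary endpoint: at least 85% for 10% versus 50%, with 30 and 20 women at two-sided 0.05 (SAP 2.4). The normal-approximation chi-square calculation gives 88.9%, so that figure holds, but it does not bear on this point.

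**Step 2. Follow the scans through the documents.**

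- A woman who stops at Week 2 and stays is scanned at Week 24, which is 24 − 2 = 22 weeks off drug.
- A woman who stops at Week 13 and stays is scanned at 24 − 13 = 11 weeks off drug.
- A woman who takes 4 weeks of drug and withdraws from the study has no PD scan under Operations Manual 3.17. One with the same 4 weeks who stays has a Week 24 scan. Follow-up status, not exposure, decides which of them contributes.
- SAP 9.5.2 removes none of these Week 24 scans unless the machine manufacturer changed.

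**Step 3. Size of the dilution.** The documents give none of the inputs, so all are assumptions: d is the share of an arm's scanned women who are off drug; w is the week of stopping; r is the share of accrued loss regained by the scan. Loss is taken as linear in time on drug and measured relative to placebo.

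Share of the on-drug 24-week loss shown by the arm mean = (1 − d) + d × (w/24) × (1 − r).

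Example: d = 20%, w = 4, r = 0 gives 0.80 + 0.20 × 4/24 = 0.833.

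| d | Week 4, r = 0 | Week 12, r = 0 | Week 18, r = 0 | Full recovery, r = 1 |
|---|---|---|---|---|
| 10% | 91.7% | 95.0% | 97.5% | 90.0% |
| 20% | 83.3% | 90.0% | 95.0% | 80.0% |
| 30% | 75.0% | 85.0% | 92.5% | 70.0% |

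The range is about 70% to 98%.

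**Step 4. In BMD units.** Assume a 2% on-drug loss, d = 20% and r = 0. The arm mean reads 2 × 0.833 = 1.67% (stopping at Week 4) or 2 × 0.90 = 1.80% (Week 12), a shift of 0.33 or 0.20 percentage points. With an assumed SD of 3%, the standard error of the difference is 3 × √(1/20 + 1/30) = 0.87 points.

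**Step 5. Does restricting to on-drug scans gain power?** Same assumptions, 20 versus 30, alpha 0.05:

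- no dilution: 63.7%
- all scans, d = 20% stopping at Week 4: 48.6%
- all scans, d = 20% stopping at Week 12: 54.7%
- on-drug scans only, 20% fewer women in both arms: 54.2%

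Under these assumptions restriction removes the dilution, but it does not reliably raise power.

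**The case against.** **The inclusion is inferred.** No sentence in SAP 9.5.2 says that off-drug scans count. The ANCOVA covers change during the Treatment Period, and neither that term nor the analysis window is defined for BMD. For the primary endpoint, SAP 8.3.1 ends the assessment months at discontinuation. This stands as a limit on certainty. It is also a reason to write the rule down.

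**All scans may be the intended analysis.** Protocol 5.6 keeps these women in follow-up expressly to limit missing efficacy and safety data, and Operations Manual 3.17 scans everyone at Week 24. That fits a treatment-policy analysis, which is legitimate. It stands as a reason to keep that analysis. The SAP does not declare the choice, though, and plans no on-treatment result beside it.

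**The plan does not break a rule of its own.** A reader might infer that the 12-week condition and the Observed Cases rule already bar these scans. They do not. The first decides whether a PD visit scan is done, and the second is an efficacy method. Likewise, the 30-day window in Operations Manual 4.2 concerns adverse-event onset, and SAP 9.2.1 does not repeat it. Either number can serve as an example of an analysis limit, but the documents do not make it one.

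**The PD visit may sometimes fall when drug stops.** Operations Manual 3.19 sets one within 2 to 7 days of stopping drug after a positive serum pregnancy test, and 6.1 links drug return to it. Some women stopping after 12 weeks could therefore have a scan near their last dose. Protocol 5.6 favours the other reading, but the documents do not settle it.

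**Restriction has its own bias.** It selects on exposure after randomisation. A nontraumatic fracture is a listed reason for withdrawal (Protocol 5.5), so the women removed may be informative about bone. This stands, and it is why the restricted set should not replace the full one.

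**Some information is already planned.** Treatment duration and discontinuations by arm (SAP 5.0 and 6.0) will show unequal stopping, and decreases of 8% or more are listed. None of these shows time off drug at the scan.

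**Conclusion.** The point holds as a gap in specification. Read as written, Week 24 scans from women who stopped drug early but stayed enter the Month 6 summary, the percent-change ANCOVA and the loss categories. No planned output isolates bone loss on treatment. The direction of bias, toward placebo, depends on elagolix lowering BMD with time on drug.

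The size cannot be taken from the documents. The 70–98% range rests on assumed stopping of 10–30%, stopping between Weeks 4 and 18, linear loss, and recovery from none to full. With an assumed 2% loss and SD of 3%, the shifts worked above are well within one standard error.

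A reader might go further and conclude that bone loss will be understated by a known amount, or that the on-drug set should be the main analysis. The documents support neither. Adding an on-treatment analysis is a cheap improvement; it does not correct an invalid one.

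**What to change.** In SAP 9.5.2, before database lock:

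1. Define the BMD analysis window in days. State what the Treatment Period means for a woman who has stopped drug, and say how Week 24 and PD visit scans map to Month 6, including when a woman has both.
2. Keep the ANCOVA and category table on all scans, and say that they include scans after discontinuation.
3. Add a prespecified on-treatment repeat of both, limited to scans within a stated interval of the last dose and with a stated minimum exposure. For example, use 30 days with an allowance for the permitted COVID-19 delay of up to 1 month (Operations Manual 3.17), so that completers scanned late are not dropped, and 12 weeks of drug.
4. List or tabulate days on drug and days off drug at each scan, by arm.

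Separately, reconcile the two wordings of the PD scan condition, at least 12 weeks of drug (3.17) and a visit at or before Week 12 (2.2), which differ at exactly Week 12.

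The cost is SAP text, one repeated analysis and one listing; no scan or visit changes. The repeat loses 3 to 6 of 20 women per elagolix arm if 15–30% stop early (0.15 × 20 = 3; 0.30 × 20 = 6). Because it selects on exposure after randomisation, it should be reported beside the all-scans result and not in its place.

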9.5.3 Pregnancy Results

Pregnancy information will be summarized by treatment group.

10.0 Overall Type-I Error Control

This is a Phase 2 proof of concept study; therefore, there will be no control of Type I error for primary, secondary, or exploratory analyses for this study.

11.0 Version History

Table 2. SAP Version History Summary

Version	Date	Summary
1.0	29 Oct 2019	Original version

12.0 References

Appendix A. Definition of Adverse Events of Special Interest

Adverse Events of Special Interest (AESI) will be identified using the following search criteria:

Item of Safety Interest	Method of Surveillance
Bone Mineral Density Loss	Osteoporosis/Osteopenia SMQ
Bone Fractures	Osteoporosis/Osteopenia SMQ
Mood and Depression-related Events	Depression and Suicide/Self-Injury SMQ
Elevated Hepatic Transaminases	Hepatic Questionnaire and the Drug-related hepatic disorders – comprehensive SMQ
